6.1 Subject Disposition

The summary of the number of subjects in the enrolled population, evaluable population, as well as those that completed the study, and withdrew from the study with reason for withdrawal will be provided. Screen Failures will be summarized for each inclusion/exclusion criteria that was not met. Summary table will also be provided by site.

6.2 Protocol Deviations

A protocol deviation is defined as an event where the Investigator or site personnel did not conduct the study according to the protocol requirements. Any and all protocol deviations must be documented regardless of whether medically justifiable, Sponsor-approved or taken to protect the subject in an emergency.

Details regarding protocol deviations will be listed for evaluable population.

6.3 Demographics and Baseline Variables

Demographics and baseline characteristics will be summarized with descriptive statistics for enrolled population. Summary statistics for categorical variables will include frequency and percentages, and for continuous variables will include mean, standard deviation (SD), minimum, median, and maximum.

The demographic variables will include:

- Age (at signing informed consent)
- Sex
- Race

6.4 Medical History/Baseline Assessments

Medical history including diagnosis for current admission and reported term for medical history will be tabulated and presented at participant-level for enrolled population.

Summary of baseline assessments includes:

- Type of VADs to be assessed per study participant
- VAD placement site location
- Number of lumens
- Type of dressing/securement
- Type and number of needle-free connector(s)
- Type and number of intravenous tubing/ extension set(s)
- Type and number of other add-on devices i.e. valves, stop cocks

6.5 Follow-up Visit Summary

Follow-up visit summary will be presented for the evaluable population.

6.6 Device Deficiency

Device deficiencies will be tabulated and presented on participant level for evaluable population. Details regarding device deficiencies will be listed.

7 Safety Analysis

An AE is defined as any untoward medical occurrence, unintended disease or injury, or untoward clinical signs (including abnormal laboratory findings) in participants, users or other persons, whether or not related to study device and whether anticipated or unanticipated (ISO 14155:2020). In this study, AE collection will be limited to those events judged to be related or likely related to the BD PureHub™ Disinfecting Cap and any events of bloodstream infection, including central line associated bloodstream infections (as defined in the List of Abbreviations).

An overall summary including the number and percentage of subjects with at least one AE, total number of AEs, total number of SAEs, AEs by relationship to the Study Device/Procedure, and AEs by severity of the event will be summarized for the enrolled population. In addition, AEs will be summarized by System Organ Class (SOC) and Preferred Term (PT):

- Number of AEs by SOC and PT
- Number of SAEs by SOC and PT
- Number of AEs by relationship to study device/procedure
- Number of AEs by severity by SOC and PT

A listing of all AEs, SAEs and UADEs will be provided for the enrolled population. An UADE is identified if answer to the question “Is the event expected” on the Adverse Events CRF page is “No”.

8 Interim Analysis Plan

No interim analysis is planned for the study.

9 References

None.

10 SAP Revision History

Version Number	Rationale for Change	Section or Page Affected	Description of Change
1.0	Original SAP		
2.0	Amendment	Section 5.3, page 8	Updated methodology for calculating number of caps per day
3.0	Amendment	Section 5.3, page 8	Updated methodology for calculating number of caps per day. The number of days for subject in study will be capped at 45 days.

11 Appendix

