# 9 ADVERSE EVENTS AND DEVICE DEFICIENCIES

## 9.1 Definitions of Events

### 9.1.1 Adverse Events (AEs)

An AE is defined as any untoward medical occurrence, unintended disease or injury, or untoward clinical signs (including abnormal laboratory findings) in participants, users or other persons, whether or not related to study device or procedure and whether anticipated or unanticipated [ISO14155:2020].

In this study, AE collection will be limited to those events judged to be related or likely related to the BD PureHub™ Disinfecting Cap and any events of bloodstream infection, including CLABSI (as defined in the List of Abbreviations).

Pre-existing conditions should be considered as part of the participant's medical history and should not be reported as an AE unless there is a substantial increase in severity or frequency of the condition, which has not been attributed to natural history. Likewise, planned hospital visits and/or hospital stays should not be considered as adverse events. Exacerbation of an existing condition should be reported as an AE if the event meets the protocol definition of an AE.

The clinical course of the event will be followed according to accepted standards of medical practice until the event resolves, stabilizes, or in the opinion of the Investigator, is no longer considered clinically significant. The Investigator must supply the Sponsor with information concerning the follow up and/or resolution of the AE.

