#### **9.1.3 Adverse Device Effect (ADE) / Serious Adverse Device Effect (SADE)**

An adverse device effect is defined as any adverse event that is considered to be related to the use of an investigational medical device. This definition includes any event resulting from insufficiencies or inadequacies in the instructions for use, deployment, implantation, installation or operation or any malfunction of the investigational device (study device) and includes any event that is a result of a user error.

A serious adverse device effect (SADE) is defined as an ADE that has resulted in any of the consequences characteristic of an SAE.

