#### **9.1.4 Unanticipated (Serious) Adverse Device Effect (UADE/USADE)**

An unanticipated (serious) adverse device effect (UADE/USADE) is any (serious) adverse device effect on health or safety or any life-threatening problem or death caused by, or associated with, a study device, which by its nature, incidence, severity, or outcome has not been identified in the current instructions for use and/or current version of the risk analysis report, or any other unanticipated serious problem associated with a device that relates to the rights, safety or welfare of participants.

UADEs/USADEs will be reported to the appropriate governing body per ISO 14155:2020.

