### 9.3 Relationship of Adverse Event to Device(s)/Procedure

Each AE will be assessed for its relationship to the study device or procedure according to the following guidelines.

- A. Assess each AE for its relationship to the device, that is, AEs directly attributable to the study device (BD PureHub™ Disinfecting Cap) used.
- B. The following categories shall be used for assigning the certainty of the relatedness.

Relatedness	Description
Not Related	Event is independent of study intervention and/or evidence exists that the event is related to another etiology. There must be an alternative etiology documented by the clinician.
Unlikely Related	Event in which the temporal relationship to study intervention makes a causal relationship improbable (e.g., the event did not occur within a reasonable time of the study device use) and in which underlying disease provides plausible explanations (e.g., the participant's clinical condition other concomitant treatments).
Likely Related	Event in which there is evidence to suggest a causal relationship and the influence of other factors is less likely. The event occurs within a reasonable time after use of the study device and is less likely to be attributed to concurrent disease.
Related	Event in which there is clear evidence to suggest a causal relationship and other possible contributing factors can be ruled out. The event occurs in a plausible time relationship to use of the study device and cannot be explained by concurrent disease.

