5.2 Primary Safety Endpoints

The primary safety endpoint is the rate of device-related adverse events. It will be calculated as the number of participants with adverse events related to device divided by total number of participants. Adverse events related to device is determined by the responses to “Relationship to study device” on the “Adverse Events” log form:

- Likely Related
- Related

95% confidence interval will be calculated using Clopper-Pearson exact method. The analysis will be performed on the enrolled population.

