5.3 Informational Endpoint(s)

The informational endpoints are:

- The number of BD PureHub™ Disinfecting Caps used per day/per study participant
- The purposes for each intended removal of the BD PureHub™ Disinfecting Cap from the needle free connector
- Incidence of central line associated bloodstream infection (CLABSI)
- Incidence of bloodstream infections

The calculation of number of PureHub caps used per day will be total number of caps used (including the ones attempted but didn’t attach) divided by number of days participants were in VAD therapy. If multiple VADs were removed, number of days will be last VAD removal date – PureHub initial placement date. If at least one VAD is not removed, the number of days will be the minimum of study duration (participant end of study date – PureHub initial placement date) and 45 days. The number of caps used will be from the following CRF pages:

- PureHub Initial Placement page, Number of caps used
- PureHub Maintenance page, Number of caps used

The purposes of removal of the BD PureHub™ Disinfecting Cap are identified on “PureHub Maintenance” log in response to “Removal reason” question. The percentage of each response will be provided, and the denominator will be the total number of intended removals.

Incidence of bloodstream infections can be identified on the CRF “Adverse Events” log form. If response to “In case of bloodstream infection, how was it confirmed” is not “Blood Stream Infection Not Present”, then subject had a bloodstream infection.

Central line associated bloodstream infection can be identified if the response to “Is the bloodstream infection central-line associated” is “Yes” on the CRF “Adverse Events” log form.

The analysis will be performed on the evaluable population. Descriptive statistics for the informational endpoints will be provided. Summary statistics for categorical variables will include frequency counts and percentages and for continuous variables will include mean, standard deviation, minimum, median, and maximum.

6 Summary of General Study Data

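### SAP Section 7 identifies a UADE from expectedness alone, so as written an unexpected bloodstream infection unrelated to the cap would be labelled a UADE in the listing

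*SAP*

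**What the plan says.** SAP Section 7 plans a listing of adverse events, serious adverse events and UADEs for the enrolled population and states how a UADE is found: "An UADE is identified if answer to the question “Is the event expected” on the Adverse Events CRF page is “No". It attaches no other condition.

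The protocol builds the term in two steps. Section 9.1.3: "An adverse device effect is defined as any adverse event that is considered to be related to the use of an investigational medical device". Section 9.1.4 then covers an unanticipated "adverse device effect on health or safety or any life-threatening problem or death caused by, or associated with, a study device", and closes with "any other unanticipated serious problem associated with a device that relates to the rights, safety or welfare of participants".

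Protocol Section 9.1.1 limits collection to events judged related or likely related to the cap, plus "any events of bloodstream infection, including CLABSI". SAP Section 7 repeats that scope, and SAP Section 5.3 says where the infections are found: "Incidence of bloodstream infections can be identified on the CRF “Adverse Events” log form".

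Protocol Section 9.3 has four relationship ratings. The lowest, 'Not Related', is described in these words: "Event is independent of study intervention and/or evidence exists that the event is related to another etiology".

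For the primary safety endpoint, SAP Section 5.2 does apply a relationship filter: "Adverse events related to device is determined by the responses to “Relationship to study device” on the “Adverse Events” log form". The qualifying answers are 'Likely Related' and 'Related'.

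**The concern.** A UADE has two parts: it is unanticipated, and it is an effect of, or associated with, the device. The SAP rule tests only the first. If only device-related events were collected, leaving out the second part would do no harm, because every event on the log would already satisfy it. This study also collects all bloodstream infections, so the log can hold events that the investigator has rated as having nothing to do with the cap.

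At stake is the accuracy of a safety label. Protocol Section 9.1.4 says that UADEs are reported to the appropriate governing body. A final listing that calls a 'Not Related' infection a UADE would contradict the protocol's definition. It could also show a UADE that was, correctly, never reported as one. The sponsor would then have to explain that discrepancy in a study meant to supply clinical data under EU regulation 2017/745.

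**Working it through.** There is no planned figure to reproduce. The check compares two classification rules.

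**Step 1: does each limb of the protocol definition need a device link?** Section 9.1.4 has three limbs:
- an adverse device effect, which Section 9.1.3 defines as related to device use;
- a life-threatening problem or death caused by or associated with a study device;
- another unanticipated serious problem associated with a device.

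All three name the device. Unexpectedness alone satisfies none of them.

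**Step 2: which events can be on the log?** Under Protocol Section 9.1.1 and SAP Section 7, an event other than a bloodstream infection must be related or likely related. A bloodstream infection enters with any of the four ratings in Protocol Section 9.3.

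**Step 3: apply both rules to events answered 'No' on expectedness.** The right-hand column uses the SAP Section 5.2 cut for device-related.

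| Relationship rating | Events that can have it | SAP Section 7 label | Unexpected and device-related |
|---|---|---|---|
| Related | infection or other | UADE | UADE |
| Likely Related | infection or other | UADE | UADE |
| Unlikely Related | infection only | UADE | not a UADE |
| Not Related | infection only | UADE | not a UADE |

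The SAP rule labels 4 of 4 ratings and the linked rule 2 of 4. The 4 − 2 = 2 ratings on which they differ can be reached only by bloodstream infections. This shows where the rules part; it does not count events.

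The 'Unlikely Related' row is the less clear-cut. That rating rules out an adverse device effect under the Section 5.2 cut, but the other two limbs of Section 9.1.4 speak of association, which is broader. The 'Not Related' row leaves no such room.

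**Step 4: is a 'No' answer plausible for an infection?** The risk table in Protocol Section 2.3.1 mentions ineffective disinfection but does not name bloodstream infection. The instructions for use and the risk analysis report, against which expectedness is judged, are not in the documents. This supports plausibility and nothing more.

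**Step 5: which outputs use the rule?** SAP Section 7 uses it for the listing. It plans no UADE rate or confidence interval. The primary safety rate has its own relationship filter in SAP Section 5.2. Reporting follows Protocol Sections 9.1.4 and 9.4, not the SAP.

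**Step 6: how many events?** This cannot be computed. The documents give neither a bloodstream infection rate nor the share of infections that would be answered 'No'. The listing covers the enrolled population, planned at up to 175 participants (SAP Section 2.1).

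**The case against.** The strongest reply is that the term carries its own device link. The SAP's abbreviation list expands UADE as an unexpected adverse device effect, so the sentence may only be naming the CRF field that makes a device effect unexpected. That is a fair account of what was probably meant. It does not rescue the text: the sentence states how a UADE is identified, gives one condition, and no other passage adds the relationship filter for this purpose. A programmer following it would leave the filter out.

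The second reply is that the harm depends on material outside the documents. The CRF might ask about expectedness only for device-related events. The derived-data specification, which SAP Section 3.2 leaves until before reporting, might add the condition. The listing shells, of which only the appendix title appears, might show relationship beside each event. This stands as a limit on the consequence. Protocol Section 9.4 requires all sections of the appropriate eCRF form to be completed for all adverse events. That makes a restricted question less likely but does not exclude it.

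The third reply is that no planned estimate changes. An unrelated infection appears in the adverse event listing in any case, and over-inclusion is the cautious direction for safety. This also stands, and it is why the point is minor.

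A reader might go further and infer that the rule inflates the device-related event rate, or that it hides device effects. The documents support neither. SAP Section 5.2 filters the primary rate separately, and an unexpected related event answered 'No' is labelled a UADE under both rules.

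**Conclusion.** Wrong as written, minor. The SAP's identification rule omits the device link that every limb of Protocol Section 9.1.4 requires, and the study's collection scope makes the omission reachable through bloodstream infections rated 'Not Related' or 'Unlikely Related'.

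The effect is confined to over-inclusion in the UADE listing for the enrolled population. Its frequency is unknown, and no range can be given from the documents.

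The conclusion about the wording rests on the text alone. The conclusion that mislabelling would follow assumes that the CRF asks the expectedness question for all logged events and that the later derivation follows the SAP sentence literally. If the CRF restricts the question to device-related events, the practical effect is zero, though the sentence would still not match the protocol.

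**What to change.** In SAP Section 7, replace the sentence with: *A UADE is identified if 'Is the event expected' is 'No' and 'Relationship to study device' is 'Likely Related' or 'Related'.* This uses the same field and cut as SAP Section 5.2.

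Also show relationship and seriousness beside every event answered 'No' in the listing. The added condition covers the adverse device effect limb. The two columns keep visible any event that might come under the broader association wording of Protocol Section 9.1.4, such as a serious unexpected infection rated 'Unlikely Related'.

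The cost is one SAP sentence, one derivation line and two listing columns. No new data are needed, and no event is lost, because all of them stay in the adverse event and serious adverse event listings already planned.

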Appendix 1 Tables/Listing/Figures Shell for Final Reporting
